### 6 ADVERSE REACTIONS

- Clinical Trials Experience
- Immunogenicity

- Immune-Related Colitis: Withhold for moderate or severe, and permanently discontinue for life-threatening colitis. (5.3)
- Immune-Related Endocrinopathies (5.4):
  - Hypophysitis: Withhold for moderate or severe and permanently discontinue for life-threatening hypophysitis.
  - Thyroid Disorders: Monitor for changes in thyroid function. Withhold for symptomatic thyroid disease.
  - Adrenal Insufficiency: Withhold for symptomatic adrenal insufficiency.
  - Type 1 Diabetes Mellitus: Withhold for  $\geq$  Grade 3 hyperglycemia.
- Immune-Related Myasthenic Syndrome/Myasthenia Gravis, Guillain-Barré or Meningoencephalitis: Permanently discontinue for any grade. (5.5)
- Ocular Inflammatory Toxicity: Withhold for moderate and permanently discontinue for severe ocular inflammatory toxicity. (5.5)
- Immune-Related Pancreatitis: Withhold for moderate or severe, and permanently discontinue for life-threatening pancreatitis, or any grade of recurring pancreatitis. (5.5)
- Infection: Withhold for severe or life-threatening infection. (5.6)
- Infusion Reaction: Interrupt or slow the rate of infusion for mild or moderate infusion reactions and discontinue for severe or life-threatening infusion reactions. (5.7)
- Embryo-Fetal Toxicity: TECENTRIQ can cause fetal harm. Advise females of reproductive potential of the potential risk to a fetus and use of effective contraception. (5.8, 8.1, 8.3)

#### ADVERSE REACTIONS

Most common adverse reactions ( $\geq 20\%$ ) in patients with locally advanced or metastatic urothelial carcinoma were fatigue, decreased appetite, nausea, urinary tract infection, pyrexia, and constipation. (6.1)

Most common adverse reactions ( $\geq 20\%$ ) in patients with metastatic non-small cell lung cancer were fatigue, decreased appetite, dyspnea, cough, nausea, musculoskeletal pain, and constipation. (6.1)

To report SUSPECTED ADVERSE REACTIONS, contact Genentech at [name] or FDA at [name] or [www.fda.gov/medwatch](http://www.fda.gov/medwatch).

#### USE IN SPECIFIC POPULATIONS

Lactation: Advise not to breastfeed. (8.2)

See 17 for PATIENT COUNSELING INFORMATION and Medication Guide.

Revised: 10/2016

## FULL PRESCRIBING INFORMATION

### 1 INDICATIONS AND USAGE

#### 1.1 Locally Advanced or Metastatic Urothelial Carcinoma

TECENTRIQ (atezolizumab) is indicated for the treatment of patients with locally advanced or metastatic urothelial carcinoma who:

- Have disease progression during or following platinum-containing chemotherapy
- Have disease progression within 12 months of neoadjuvant or adjuvant treatment with platinum-containing chemotherapy

This indication is approved under accelerated approval based on tumor response rate and durability of response. Continued approval for this indication may be contingent upon verification and description of clinical benefit in confirmatory trials [*see Clinical Studies (14.1)*].

#### 1.2 Metastatic Non-Small Cell Lung Cancer

TECENTRIQ is indicated for the treatment of patients with metastatic non-small cell lung cancer (NSCLC) who have disease progression during or following platinum-containing chemotherapy. Patients with EGFR or ALK genomic tumor aberrations should have disease progression on FDA-approved therapy for these aberrations prior to receiving TECENTRIQ [*see Clinical Studies (14.2)*].

### 2 DOSAGE AND ADMINISTRATION

#### 2.1 Recommended Dosing

The recommended dose of TECENTRIQ is 1200 mg administered as an intravenous infusion over 60 minutes every 3 weeks until disease progression or unacceptable toxicity. If the first infusion is tolerated, all subsequent infusions may be delivered over 30 minutes. Do not administer TECENTRIQ as an intravenous push or bolus.

#### 2.2 Dose Modifications

No dose reductions of TECENTRIQ are recommended.

Withhold TECENTRIQ for any of the following:

- Grade 2 pneumonitis [*see Warnings and Precautions (5.1)*]
- Aspartate aminotransferase (AST) or alanine aminotransferase (ALT) greater than 3 and up to 5 times upper limit of normal (ULN) or total bilirubin greater than 1.5 and up to 3 times ULN [*see Warnings and Precautions (5.2)*]
- Grade 2 or 3 diarrhea or colitis [*see Warnings and Precautions (5.3)*]
- Symptomatic hypophysitis, adrenal insufficiency, hypothyroidism, hyperthyroidism, or Grade 3 or 4 hyperglycemia [*see Warnings and Precautions (5.4)*]
- Grade 2 ocular inflammatory toxicity [*see Warnings and Precautions (5.5)*]
- Grade 2 or 3 pancreatitis, or Grade 3 or 4 increases in amylase or lipase levels (greater than 2.0 times ULN) [*see Warnings and Precautions (5.5)*]
- Grade 3 or 4 infection [*see Warnings and Precautions (5.6)*]
- Grade 2 infusion-related reactions [*see Warnings and Precautions (5.7)*]
- Grade 3 rash

TECENTRIQ may be resumed in patients whose adverse reactions recover to Grade 0–1.

Permanently discontinue TECENTRIQ for any of the following:

- Grade 3 or 4 pneumonitis [*see Warnings and Precautions (5.1)*]
- AST or ALT greater than 5 times ULN or total bilirubin greater than 3 times ULN [*see Warnings and Precautions (5.2)*]
- Grade 4 diarrhea or colitis [*see Warnings and Precautions (5.3)*]
- Grade 4 hypophysitis [*see Warnings and Precautions (5.4)*]
- Myasthenic syndrome/myasthenia gravis, Guillain-Barré or meningoencephalitis (all grades) [*see Warnings and Precautions (5.5)*]
- Grade 3 or 4 ocular inflammatory toxicity [*see Warnings and Precautions (5.5)*]
- Grade 4 or any grade of recurrent pancreatitis [*see Warnings and Precautions (5.5)*]
- Grade 3 or 4 infusion-related reactions [*see Warnings and Precautions (5.7)*]
- Grade 4 rash

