**Table 2: Clinical Safety Laboratory Panels**

Hematology	Serum Chemistry	Urinalysis (dipstick)

 
WBC with differential (including neutrophils, basophils, eosinophils, lymphocytes, monocytes)
 
hemoglobin
 
hematocrit
 
platelet count
 
MCV
 
	
 
albumin
 
amylase
 
alkaline phosphatase
 
ALT
 
AST
 
bicarbonate
 
BUN
 
calcium
 
chloride
 
creatinine
 
GGT
 
glucose (random)
 
magnesium
 
phosphorous
 
potassium
 
sodium
 
total bilirubin
 
total protein
 
TSH
 
	
 
appearance
 
color
 
pH
 
specific gravity
 
ketones
 
leukocytes
 
protein
 
glucose
 
bilirubin
 
urobilinogen
 
occult blood (microscopic examination of sediment will be performed only if the results of the urinalysis dipstick evaluation are positive)
 

Coagulation		

 
PT
 
INR
 
APTT
 
		
Serum pregnancy test (women of childbearing potential)		Virology screen

 
βHCG
 
		
 
HIV 1 and 2 antigen/antibody combination immunoassay
 
HBV surface antigen
 
HCV RNA testing
 

WBC = white blood cell count; PT = prothrombin time; INR = international normalized ratio; APTT = activated partial thromboplastin time; ALT = alanine aminotransferase; AST = aspartate aminotransferase; BUN = blood urea nitrogen; GGT = gamma glutamyl transferase; MCV = mean corpuscular volume; TSH = thyroid stimulating hormone; βHCG= β human chorionic gonadotropin; HIV = human immunodeficiency virus; HBV = hepatitis B virus; HCV = hepatitis C virus

1. In the case of grade 3-4 laboratory abnormalities, and any clinically significant lab findings which potentially meet the definition of DLT, repeat tests must be performed every 1-2 days in order to verify duration accurately and observe recovery.

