### 8.2. Inclusion Criteria

Patients will be included if they meet the following criteria:

1. Age  $\geq$  18 years.
2. Diagnosis of metastatic lung cancer, with:
  - a. Histologic confirmation of the primary NSCLC histology
  - b. At least one lesion amenable for intra-tumoral injection of MV-NIS.
3. Patient meets the FDA-approved indication for atezolizumab treatment in NSCLC ([Tecentriq® USPI 2016](#)).
4. Patient may have more than one site of recurrence/metastatic disease but only one lesion will be injected that is  $\geq$  1 cm in size (if in the lung, the lesion must be  $\geq$  2 cm and adjacent to the pleura).
5. Measurable disease per RECIST 1.1.
6. ECOG Performance Status (PS) 0 or 1.
7. Ability to provide informed consent.
8. Willingness to comply with all required protocol procedures including providing biologic specimens, participating in the SPECT/CT imaging and returning to the clinical study site for follow up visits.
9. Life expectancy of more than 12 weeks (in the opinion of the enrolling investigator).
10. The following laboratory values obtained  $\leq$  14 days prior to registration.
  - a. ANC  $\geq$  1500/mm^3
  - b. Platelets  $\geq$  100,000/mm^3
  - c. HgB  $>9.0$  g/dL
  - d. Total bilirubin  $\leq$  institutional upper limit of normal (ULN)
  - e. SGOT (AST)  $\leq$  2.5 x ULN
  - f. Creatinine  $\leq$  1.5 x ULN
11. Must be willing to implement contraception throughout study and for the 8 weeks following last study drug administration.

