### **9.1.7. Dose Modifications and Delays for Toxicity Related to Study Drug**

Since there is only one dose of MV-NIS administered per patient, there are no dose modifications or delays in this study for MV-NIS. If the patient experiences an acute injection or procedure related reaction the procedure should be abandoned and supportive care provided. If study drug administration is abandoned due to technical reasons not associated with an AE, the procedure may be reattempted at another time at the investigators discretion. Consult the medical monitor regarding reassessment of eligibility in such cases.

Dose modifications and delays for atezolizumab should be based on the approved [Tecentriq® US Package Insert](#).

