#### 13.1.1. Analysis populations

Safety Population: The safety population consists of all patients who receive at least one dose of the study medication. All safety and tolerability evaluations will be based on this analysis set.

PK/PD Population: The PK/PD population includes all patients without protocol deviations affecting interpretability of PK and/or PD.

Efficacy Population: primary efficacy analyses will utilize the treated population at the MTD, meaning all patients who receive at least 1 dose of study drug at the MTD; an additional analysis will include all treated patients, which is identical to the Safety Population.

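### Eligibility limits AST and bilirubin but not ALT (or amylase), so a patient may be injected with MV-NIS at a screening value for which the adopted atezolizumab label, read by value, would withhold or, for ALT, stop the second drug

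*Combined protocol and SAP*

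**What the plan says.** Inclusion criterion 10 (synopsis, section 4, repeated in section 8.2) opens "The following laboratory values obtained" and covers a window of 14 days before registration. It lists ANC, platelets, hemoglobin, total bilirubin, AST and creatinine. The liver limits are "SGOT (AST) $\leq$ 2.5 x ULN" and, for total bilirubin, the "institutional upper limit of normal (ULN"). ALT and amylase are not on the list.

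Both are measured. The serum chemistry column of Table 2 includes "amylase alkaline phosphatase ALT", and Table 1 schedules that panel within the same 14 days.

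Section 9.1.7 states: "Dose modifications and delays for atezolizumab should be based on the approved" US package insert, which is reproduced as Appendix 2. Label section 2.2 withholds for "Aspartate aminotransferase (AST) or alanine aminotransferase (ALT) greater than 3 and up to 5 times upper limit of normal (ULN", with a parallel bilirubin rule above 1.5 and up to 3 x ULN. It permanently discontinues for "AST or ALT greater than 5 times ULN or total bilirubin greater than 3 times ULN". For amylase or lipase it withholds at Grade 3 or 4 (above 2.0 x ULN), and label section 5.5 allows resumption on improvement.

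MV-NIS is given once, on Day 1, and atezolizumab starts on Day 15. Section 13.1.1 bases the primary efficacy analysis on "all patients who receive at least 1 dose of study drug at the MTD".

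**The concern.** Two of the three liver tests that the label acts on are limited at entry and the third is not. ALT stands in the same label bullets as AST, so its absence from criterion 10 looks like an omission rather than a choice.

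The sequence gives the gap its weight. The injection cannot be undone, and it comes two weeks before the drug that the label rules govern. A patient who qualifies with a high ALT may undergo the injection and the biopsies and then not be given the second half of the regimen on time, or at all. The primary objective is the MTD of the combination, and the 45% target response rate is for the combination. Such a patient informs neither well but is still counted in the efficacy denominator.

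**Working it through.** **Step 1. Entry limits against label thresholds (multiples of ULN).**

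| Test | Entry limit (section 8.2) | Label withholds above | Label permanently stops above | Can an eligible screening value cross? |
|---|---|---|---|---|
| AST | 2.5 | 3 | 5 | No (2.5 < 3) |
| Total bilirubin | 1.0 | 1.5 | 3 | No (1.0 < 1.5) |
| ALT | none | 3 | 5 | Yes, both |
| Amylase | none | 2.0 (Grade 3-4) | no amylase value | Yes, withhold only |

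Example: AST 2 x ULN with ALT 4 x ULN meets criterion 10 and lies in the label's withhold range. With ALT 6 x ULN the patient still meets criterion 10 and lies in the permanent-stop range.

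**Step 2. Do other criteria close the gap?** Exclusion 5 removes patients who have not recovered from effects of prior systemic therapy. It does not reach a raised ALT from liver metastases, other drugs or liver disease. Exclusion 16 leaves co-morbid illness to the investigator's judgment and sets no laboratory value. Inclusion 3 concerns the indication, not laboratory results.

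**Step 3. Would the schedule catch it before injection?** As Table 1 reads, chemistry is due within 14 days before registration, on Day 8 and on Day 36. Nothing is marked on Day 1 or Day 15. The first scheduled repeat therefore follows the injection, and Day 8 is the last scheduled value before the first infusion.

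**Step 4. The plan's own design figures.** Section 13.1 requires at least 8 responses in 21, with a null of 20% and a target of 45%. With X binomial:

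- P(X >= 8; n = 21, p = 0.20) = 0.04305, against the stated 0.043.
- P(X >= 8; n = 21, p = 0.45) = 0.80293, against the stated 80.29%.

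Both reproduce.

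**Step 5. Illustration of the stake.** Assume that k of the 21 are injected, never receive atezolizumab, do not respond and are not replaced, and that the others respond at 45%. Power is then P(X >= 8; n = 21 - k, p = 0.45):

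- k = 0: 80.3%
- k = 1 (n = 20): 74.8%
- k = 2 (n = 19): 68.3%

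The documents give no value for k. If a fraction q of enrolled patients were affected, the chance of at least one among 21 is 1 - (1 - q)^21. For assumed q of 1%, 2% and 5% this is 19%, 35% and 66%. These q values are assumptions that show a range, not estimates.

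**The case against.** The strongest reply is that label section 2.2 manages reactions during treatment and does not set conditions for starting it. The label lists no contraindications. Withheld treatment may resume after recovery to Grade 0-1. Label section 5.2 defines immune-mediated hepatitis as having no other clear cause, and liver metastases or pre-existing liver disease would be another cause. A screening value also need not persist to Day 15. This stands against a stronger inference that a reader might draw, that such a patient is already barred from atezolizumab at entry. The documents do not say so. What remains is that section 9.1.7 adopts rules written as laboratory values, without saying how they apply to a value that was high before treatment.

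Three further inferences also fail:

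- **Amylase as a permanent stop.** The label only withholds on an amylase value. Its permanent pancreatic stop is for Grade 4 or recurrent pancreatitis.
- **A lost third of a 3-patient dose cohort.** Section 7.1.2 replaces patients who do not complete the initial course for reasons other than adverse events or progression, and section 8.5 also permits replacement. Section 11.2 does not count an unworsened pre-existing laboratory abnormality as an adverse event. Section 7.1.2 does not spell out whether both drugs must be given, so replacement is likely rather than certain. It would not take the patient out of the Efficacy Population.
- **A high baseline ALT readily producing a DLT.** A DLT must be at least possibly attributed to MV-NIS and not be pre-existing because of the malignancy.

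The existing safeguards also count for something. The approved indication requires progression during or after platinum chemotherapy, so exclusion 5 is relevant to every patient, and the medical monitor receives the eligibility data before registration. These narrow the gap, but none sets an ALT limit.

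**Conclusion.** The mismatch is real and narrow. AST and bilirubin are held below the adopted label's withhold levels at entry, while ALT is unrestricted and can lie above both the withhold and the permanent-stop level. Amylase is a weaker second case because its rule is reversible. A patient may be injected in that state and remain in the efficacy analysis without ever receiving the combination.

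That conclusion comes from comparing the documents' own figures and needs no assumption beyond reading the label bullets by value. The size does need assumptions. The falls to 74.8% and 68.3% require that the patient never receives atezolizumab, does not respond and is not replaced. For ALT between 3 and 5 x ULN or for amylase, the first of these may well fail, since withholding can be lifted. The second is not certain either, since section 5.1.2 reports that several patients had a response or stabilization on MV-NIS. The figures should not be read as an expected loss of power. This is a cheap improvement to the eligibility list, not a flaw that undermines the design.

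**What to change.** Reconcile inclusion 10e, in both section 4 and section 8.2, with label section 2.2 so that ALT is addressed alongside AST. Have the clinical team decide whether amylase needs the same treatment. Any numeric limits are for the clinical team, and none is proposed here.

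The change should stay specific to these tests. A blanket line excluding any screening value that meets a label withhold criterion would set a clinical rule. It would also reach Grade 3-4 hyperglycemia and could conflict with exclusion 8, which expressly allows type 1 diabetes.

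The cost is one eligibility line in an amendment, with no new test because the screening panel already includes ALT and amylase. The downside is an occasional extra screen failure.

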## 2.3 Preparation and Administration

### Preparation

Visually inspect drug product for particulate matter and discoloration prior to administration whenever solution and container permit. TECENTRIQ is a colorless to slightly yellow solution. Discard the vial if the solution is cloudy, discolored, or visible particles are observed. Do not shake the vial.

Prepare the solution for infusion as follows:

- Withdraw 20 mL of TECENTRIQ from the vial.
- Dilute into a 250 mL polyvinyl chloride (PVC), polyethylene (PE), or polyolefin (PO) infusion bag containing 0.9% Sodium Chloride Injection, USP.
- Dilute with 0.9% Sodium Chloride Injection only.
- Mix diluted solution by gentle inversion. Do not shake.
- Discard used or empty vials of TECENTRIQ.

### Storage of Infusion Solution

This product does not contain a preservative.

Administer immediately once prepared. If diluted TECENTRIQ infusion solution is not used immediately, it can be stored either:

- At room temperature for no more than 6 hours from the time of preparation. This includes room temperature storage of the infusion in the infusion bag and time for administration for infusion.
- Under refrigeration at 2°C–8°C (36°F–46°F) for no more than 24 hours.

Do not freeze.

Do not shake.

### Administration

Administer the initial infusion over 60 minutes through an intravenous line with or without a sterile, non-pyrogenic, low-protein binding in-line filter (pore size of 0.2–0.22 micron). If the first infusion is tolerated, all subsequent infusions may be delivered over 30 minutes.

Do not co-administer other drugs through the same intravenous line.

### **3 DOSAGE FORMS AND STRENGTHS**

Injection: 1200 mg/20 mL (60 mg/mL) colorless to slightly yellow solution in a single-dose vial.

### **4 CONTRAINDICATIONS**

None.

### **5 WARNINGS AND PRECAUTIONS**

#### **5.1 Immune-Related Pneumonitis**

Immune-mediated pneumonitis or interstitial lung disease, defined as requiring use of corticosteroids and with no clear alternate etiology, occurred in patients receiving TECENTRIQ. Monitor patients for signs with radiographic imaging and for symptoms of pneumonitis. Administer steroids at a dose of 1 to 2 mg/kg/day prednisone equivalents for Grade 2 or greater pneumonitis, followed by corticosteroid taper. Withhold TECENTRIQ until resolution for Grade 2 pneumonitis. Permanently discontinue TECENTRIQ for Grade 3 or 4 pneumonitis [*see Dosage and Administration (2.2)*].

Across clinical trials, 2.6% (51/1978) of patients developed pneumonitis. Fatal pneumonitis occurred in two patients.

#### **Urothelial Carcinoma**

In 523 patients with urothelial carcinoma who received TECENTRIQ, pneumonitis occurred in six (1.1%) patients. Of these patients, there was one patient with fatal pneumonitis, one patient with Grade 3, three patients with Grade 2, and one patient with Grade 1 pneumonitis.

TECENTRIQ was held in all cases and five patients were treated with corticosteroids.

Pneumonitis resolved in three patients. The median time to onset was 2.6 months (range: 15 days to 4.2 months). The median duration was 15 days (range: 6 days to 3.1+ months).

#### **NSCLC**

In 1027 patients with NSCLC who received TECENTRIQ, pneumonitis occurred in 38 (3.7%) patients. Of these patients, there was one patient with fatal pneumonitis, two patients with Grade 4, thirteen patients with Grade 3, eleven patients with Grade 2, and eleven patients with Grade 1 pneumonitis. TECENTRIQ was held in 24 patients and 21 patients were treated with corticosteroids. Pneumonitis resolved in 26 of the 38 patients. The median time to onset was 3.3 months (range: 3 days to 18.7 months). The median duration was 1.4 months (range: 0 days to 12.6+ months).

#### **5.2 Immune-Related Hepatitis**

Immune-mediated hepatitis, defined as requiring use of corticosteroids and with no clear alternate etiology, occurred in patients receiving TECENTRIQ treatment. Liver test abnormalities occurred in patients who received TECENTRIQ. Monitor patients for signs and symptoms of hepatitis. Monitor AST, ALT, and bilirubin prior to and periodically during treatment with TECENTRIQ. Administer corticosteroids at a dose of 1–2 mg/kg/day prednisone equivalents for Grade 2 or greater transaminase elevations, with or without concomitant elevation in total bilirubin, followed by corticosteroid taper. Withhold TECENTRIQ for Grade 2 and permanently discontinue TECENTRIQ for Grade 3 or 4 immune-mediated hepatitis [*see Dosage and Administration (2.2) and Adverse Reactions (6.1)*].

Across clinical trials (n=1978), Grade 3 or 4 elevation occurred in ALT (2.5%), AST (2.3%), and total bilirubin (1.6%).

#### **Urothelial Carcinoma**

In patients with urothelial carcinoma (n=523), Grade 3 or 4 elevation occurred in ALT (2.5%), AST (2.5%), and total bilirubin (2.1%). Immune-mediated hepatitis occurred in 1.3% of patients. Of these cases, one patient died from hepatitis, five patients had Grade 3, and one

patient had Grade 2 hepatitis. The median time to onset was 1.1 months (range: 0.4 to 7.7 months). TECENTRIQ was temporarily interrupted in four patients; none of these patients developed recurrence of hepatitis after resuming TECENTRIQ.

